12.2.6 Neurocognitive Functioning and Mental Health

The analysis of cognitive and mental health outcomes will focus on the trajectories of cognitive functioning and mental health, and the trajectories of co-occurring risks in cognitive, mental health and behavioral health. Cognitive outcomes (executive functioning, processing speed, episodic and working memory, attention, etc.) will be evaluated both as continuous and binary measures. Mental health outcomes (depression, PTSD, and anxiety) and behavioral health outcomes will be evaluated as binary measures. Group-based trajectory and multi-trajectory models will be used to identify trajectories of

single and co-occurring outcomes. Factors to be evaluated for their association with single and co-occurring trajectories will include PHIV status, individual, interpersonal, systemic and structural influences experienced during childhood and adolescence, including adverse childhood experiences (e.g., exposure to violence, neglect, etc.) and young adulthood experiences (e.g., racism, low levels of social support, etc.), as well as historical [from AMP] information on caregiver cognition, education, etc.).

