2.2.6 Neurocognitive Functioning and Mental Health

Specific Aims:

- Among YAPHIV and YAPHEU, to describe the trajectories of cognitive functioning and mental health in young adulthood and examine factors associated with these trajectories.
- To identify the trajectories of co-occurring risks in cognitive, mental health, and behavioral health (sexual behaviors and drug and alcohol use) in young adulthood.
- To identify factors associated with trajectories of co-occurring risks in cognitive, mental, and behavioral health in young adulthood, including PHIV status, and individual, interpersonal, systemic and structural influences experienced during childhood and adolescence, including adverse childhood experiences (e.g., exposure to violence, neglect, etc.) and young adulthood experiences (e.g., racism, low levels of social support, etc.).
- To define the impact of the SARS-CoV-2 pandemic and its associated mitigation strategies on the mental health of participants affected by HIV.

Hypotheses:

- YAPHIV will demonstrate lower cognitive abilities than YAPHEU and young adults without PHIV exposure when compared to national norms for young adults.
- Unique trajectories of cognitive, mental health, and behavioral risk in adulthood will be associated with youth, family, and community influences experienced during childhood and adolescence.
- YAPHIV with advanced disease will demonstrate cognitive vulnerabilities in executive functioning, processing speed, and working memory compared to healthier YAPHIV and YAPHEU.
- YAPHIV will exhibit higher rates of mental health problems relative to the normative population, but these rates will be similar to YAPHEU.
- Among YAPHIV, prevalence and severity of mental health problems will be higher among those with prior and/or current evidence of nonadherence and immune dysfunction (low CD4 cell count, detectable HIV RNA viral load) during adolescence and young adulthood.
- Participants will report SARS-CoV-2 pandemic-related stress, with effects more pronounced among those with a history of psychiatric or substance use. Participants who report closely following pandemic-related mitigation strategies will be more likely to report depressive symptoms and negative emotions than participants not closely following these strategies.

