The Client Diagnostic Questionnaire (CDQ) will be conducted in-person every 3 years starting at Year 3 (e.g., Years 3, 6, 9, 12, ...). The CDQ is a psychiatric screening tool designed and validated for populations affected by HIV (Aidala et al., 2004). The CDQ is a structured interview used to identify current symptoms of psychiatric disorder(s), including depression, anxiety, PTSD, and psychosis, as well as alcoholic and nonalcoholic substance abuse. The CDQ will be administered by a trained psychologist. Training will be conducted for the psychologist. The CDQ was used in AMP for caregivers only, and the same procedure for monitoring consistency in administration used in AMP will be used in AMP Up.

The Patient Health Questionnaire-9 (PHQ-9) and Generalized Anxiety Disorder 7-Item Scale (GAD-7) will be administered as an interview at Entry. After Entry, the PHQ-9 and the GAD-7 will be administered through the web-based survey. The PHQ is a self-administered version of the Primary Care Evaluation of Mental Disorders (PRIME-MD) diagnostic instrument for common mental disorders. The PHQ-9 is the depression module of the PHQ, and scores each of the 9 DSM-IV criteria as “0” (not at all) to “3” (nearly every day). PHQ-9 scores of 5, 10, 15, and 20 represented mild, moderate, moderately severe, and severe depression, respectively. The PHQ-9 is considered a reliable and valid screening of depression severity. The GAD-7 is a brief, psychometrically sound screener that identifies presence and severity of generalized anxiety disorder symptoms in adults (Spitzer et al., 2006). The Primary Care PTSD Screen for DSM-5 (PC-PTSD-5) is a 5-item screen designed to identify individuals with probable PTSD (Prins et al., 2016).

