12.1.1 Comparisons between YAPHIV and YAPHEU

For continuous outcomes, the sample size of 650 YAPHIV vs. 200 YAPHEU provides 80% power to detect a difference in means of 0.227 standard deviations based on a 2-sample t-test (assuming normality holds), and 0.240 based on a non-parametric Wilcoxon rank sum test (for skewed outcomes) at alpha = 0.05. For example, if the full-scale IQ scores of YAPHIV is compared with YAPHEU and a standard deviation of 15 points is assumed, a difference of 3.40 points or more in the mean IQs could be detected. Assuming loss to follow-up and/or incomplete/missing assessments of 4% per year for infected and 6% per year for uninfected participants at two years after enrollment into AMP Up is completed, then an adjusted sample size of 415 YAPHIV vs. 101 YAPHEU provides 80% power to detect a difference of 0.311 standard deviations, or 4.67 points in mean IQ scores. Once adjusted for potential confounders, some power will typically be lost so the minimum detectable difference will usually increase.

For binary outcomes, the table below shows the minimum difference that can be detected in proportions in terms of the Odds Ratio (OR) based on comparing YAPHIV vs. YAPHEU, at 80% power with a 0.05 significance level. For this type of outcome, the detectable differences depend on the underlying rate of the event in the comparison cohort. For simplicity here, it is assumed that the event rate is higher in the YAPHIV cohort than the YAPHEU cohort.

Table 12.1. Minimum detectable ORs between YAPHIV and YAPHEU at 80% power and a 0.05 significance level for various event rates in the comparison cohort

Sample Size for YAPHIV Cohort	Sample Size for YAPHEU Cohort	Event rate in YAPHEU Cohort	Minimum Detectable OR	Detectable Rate in YAPHIV Cohort
650	200	4%	2.92	10.8%
		5%	2.64	12.2%
		10%	2.05	18.6%
		20%	1.73	30.2%
		30%	1.63	41.0%
415	101	4%	4.36	15.4%
		5%	3.79	16.6%
		10%	2.68	22.9%
		20%	2.13	34.7%
		30%	1.95	45.5%

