12.2.9 Transition to Adult Functioning and QoL

We will estimate the prevalence of successful transition to adult functioning (including educational attainment, employment, and independent living), health-related QoL [SF-20], HIV-related stigma, mental health [CDQ, PHQ-9, and GAD-7], PTSD [Primary Care PTSD Screen for DMS-V], self-efficacy, life satisfaction, and friendship [from NIH Toolbox emotion domain] at each follow-up visit. Prevalence of milestones associated with successful adult function (including employment, educational attainment [e.g., high school diploma or general educational development (GED), enrollment in college or certificate program], independent living) will be calculated as the number of participants with each specific outcome at each visit, divided by the total number of participants who have a measure for each outcome at that

visit. The number and proportion of young adults who have met most or all of these milestones by specific ages will be estimated. The proportion of participants with psychiatric disorders and with depression (PHQ-9), anxiety (GAD-7), and PTSD will also be estimated. The 95% CIs for each prevalence estimate will be calculated. The median (interquartile range) and mean (standard deviation) scores for health-related QoL (SF-20), HIV-related stigma, self-efficacy, life satisfaction, and friendship will be calculated.

We will compare successful transition to adult functioning and QoL by perinatal HIV status and other factors using chi-square tests and Wilcoxon rank sum tests as appropriate. Factors associated with successful transition to adult function and with QoL will be further examined with univariable and multivariable logistic and linear regression models.

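### PHQ-9 and GAD-7 scores are collected, yet depression and anxiety are analysed only as yes/no outcomes, so the severity hypothesis has no matching analysis

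*Protocol*

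**What the plan says.** Section 12.2.6 says of depression, PTSD, anxiety and behavioural health: "Mental health outcomes (depression, PTSD, and anxiety) and behavioral health outcomes will be evaluated as binary measures". The sentence before it says that cognitive outcomes "will be evaluated both as continuous and binary measures". The two groups of outcomes are therefore treated differently by explicit statement.

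Section 12.2.9 is consistent with this. For the screening instruments it says "The proportion of participants with psychiatric disorders and with depression (PHQ-9), anxiety (GAD-7), and PTSD will also be estimated", while it plans medians and means for quality of life, stigma, self-efficacy, life satisfaction and friendship.

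Section 9.3 describes both instruments as graded. On depression: "PHQ-9 scores of 5, 10, 15, and 20 represented mild, moderate, moderately severe, and severe depression, respectively". On anxiety, the GAD-7 "identifies presence and severity of generalized anxiety disorder symptoms in adults". Both are given by interview at Entry, and then: "After Entry, the PHQ-9 and the GAD-7 will be administered through the web-based survey".

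Among the section 2.2.6 hypotheses is that, within YAPHIV, "prevalence and severity of mental health problems will be higher among those with prior and/or current evidence of nonadherence" and of immune dysfunction.

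**The concern.** The hypothesis about YAPHIV with nonadherence or immune dysfunction has two parts, prevalence and severity. A single yes/no outcome per condition answers the first. It cannot distinguish a participant just above the cut from one far above it, or one just below it from one without symptoms. The scores that would answer the second part are collected at Entry and in follow-up, but no analysis in section 12 uses them as scores.

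Dichotomising also costs precision. Where the score shifts between groups without many participants crossing the cut, the binary analysis needs a larger shift for the same power. At stake is how well the study can detect graded associations of mental health with adherence, CD4 count and viral load within YAPHIV.

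**Working it through.** **1. The protocol's figures reproduce** (two-sided alpha 0.05, 80% power).

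- Continuous (12.1.1): d = (1.960 + 0.842) × √(1/n₁ + 1/n₀). For 650 and 200 this gives 2.802 × 0.0809 = 0.227. For 415 and 101 it gives 0.311. Both match the text: the study "provides 80% power to detect a difference in means of 0.227 standard deviations based on a 2-sample t-test" at full size, and 0.311 SD after attrition. For skewed outcomes the protocol gives 0.240 SD at 650/200.
- Binary (Table 12.1): a Wald test on the log odds ratio, ln(OR) / √[1/(n₀p₀q₀) + 1/(n₁p₁q₁)], should equal 2.802. At 650/200 with p₀ = 20% and OR 1.73, p₁ = 0.346/1.146 = 0.302. Then ln(1.73) = 0.548, the standard error is √(0.03125 + 0.00730) = 0.196, and the ratio is 2.79, which is 79.7% power. All ten rows reproduce this way, with power between 79.7% and 80.3%.

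**2. Put both on one scale.** Assume a normal underlying score cut at a threshold. A pair of rates then corresponds to a shift of z(p₁) − z(p₀) SD. The sample factor is (binary shift / continuous shift)², and the share of the sample lost is 1 − 1/factor. For the 20% row the shift is −0.519 + 0.842 = 0.323 SD, the factor is (0.323/0.227)² = 2.02, and the loss is 51%.

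| Rate in YAPHEU | Shift needed, 650/200 | Factor vs 0.227 SD | Loss vs 0.227 SD | Loss vs 0.240 SD | Loss at 415/101 vs 0.311 SD |
|---|---|---|---|---|---|
| 4% | 0.516 | 5.2 | 81% | 78% | 82% |
| 5% | 0.480 | 4.5 | 78% | 75% | 79% |
| 10% | 0.387 | 2.9 | 66% | 62% | 67% |
| 20% | 0.323 | 2.0 | 51% | 45% | 52% |
| 30% | 0.300 | 1.7 | 43% | 36% | 43% |

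At 650/200 the loss equals one half at a comparison rate of 20.8% against 0.227 SD, and at 16.4% against 0.240 SD. If the true shift were 0.227 SD, a two-proportion test would have 37%, 51% and 57% power at 10%, 20% and 30%, against 80% for the score.

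**3. The comparison that matters for severity is within YAPHIV.** The same step applies to Tables 12.2 and 12.3. For a 50/50 split at N = 650 and a 20% rate, OR 1.68 gives p₁ = 0.336/1.136 = 0.296 and a shift of 0.305 SD, against 0.220 SD for the score. The loss is 1 − (0.220/0.305)² = 48%.

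| Rate in group 2 | Loss, 50/50 split | Loss, 20/80 split |
|---|---|---|
| 10% | 61% | 66% |
| 20% | 48% | 52% |
| 40% | 37% | 38% |

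At N = 415 the losses are within about one percentage point of these.

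**The case against.** Several objections have force.

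- **Size.** A reader might infer that the protocol's own power figures show half or more of the sample being wasted. They do not. The protocol never compares the two scales. The comparison needs an assumption it does not state, a normal score with a pure shift and one cut, whereas PHQ-9 and GAD-7 are short, bounded and likely skewed. The loss is 43% at a 30% comparison rate, and 45% at 20% against the skewed-outcome figure. No depression or anxiety rate is given. Section 1.1 describes mental health problems as frequent in both groups, which, if anything, points to the rows with the smaller losses.
- **Comparison with YAPHEU.** A reader might also infer that a conclusion of similarity to YAPHEU is undermined. Section 2.2.6 frames that hypothesis in terms of rates, so a binary outcome is the right match, and a mean-score analysis would answer a different question.
- **Models.** Section 12.2.6 plans trajectory models. Tables 12.1 to 12.3 describe single comparisons, and section 12.1.2 notes that repeated measures give more power. The factors do not transfer directly.
- **Severity.** Binary outcomes at higher PHQ-9 cuts would separate severe cases, though coarsely. The CDQ is a further source for depression and anxiety and suits a yes/no outcome.
- **Level of detail.** An extra analysis could be left to an analysis plan.

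The first three limit the size and reach of the point, and the verdict adopts them. The fourth softens it, but no severity-graded outcome is planned. The last does not remove it: 12.2.6 is not silent, since it fixes the form of the mental health outcomes and contrasts it with that of cognition.

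**Conclusion.** The point holds as a mismatch between a stated hypothesis and the stated analysis. Severity within YAPHIV is hypothesised and graded scores are collected, but sections 12.2.6 and 12.2.9 provide only binary outcomes and proportions. This needs no power calculation.

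The loss of precision is secondary and conditional. Assuming a roughly normal underlying score and a simple two-group comparison, it is about 35% to 80% of the effective sample over the rates in the protocol's tables. It reaches half only at comparison rates of about 20% or lower, or about 16% or lower against 0.240 SD. Which rate applies cannot be told from the protocol. The point does not extend to PTSD, and it does not call for dropping the binary outcomes. It is a cheap improvement to the plan, not a defect in the comparison of rates between cohorts.

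**What to change.** In section 12.2.6, add PHQ-9 and GAD-7 total scores as continuous or ordinal outcomes alongside the binary ones, as is already done for cognition. Use mixed, ordinal or rank-based models, because the scores are likely to be skewed. Name the within-YAPHIV severity hypothesis as their main purpose. Keep the binary outcomes for prevalence and for the YAPHIV versus YAPHEU comparison of rates.

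The cost is a little more analysis and one more set of outcomes to report in a study that already has many. No new data, visits or participant burden are involved.

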12.2.7 Health Care Behaviors and Transition to Adult Health Care

To address the specific aims and hypotheses regarding adherence and health care, the proportion with suboptimal ART adherence (e.g., last missed taking their ARV medication in the past seven days), and the proportion with a gap in ARV use, at entry and follow-up among YAPHIV who provide information on ARV use will be calculated with 95% CIs. Logistic regression methods will be used to identify and evaluate factors associated with nonadherence to ART and nonadherence to health care. For analyses of changes in adherence over time GEEs will be used. Factors associated with transition to adult health care and clinical outcomes (including changes in CD4 cell count and viral load) will be identified using logistic and linear regression models. Factors of interest for these outcomes include a site- or participant-specific transition plan, social support, psychosocial resources, stressful life events, and neurocognitive functioning. The trajectories of cognitive, mental health and behavioral health during adolescence among AMP Up participants previously followed in AMP with group-based trajectory models will be described.

12.2.8 Risk and Protective Behaviors

The analysis of behaviors will focus on estimating the prevalence at study entry and over follow-up of vaginal and anal sexual intercourse, condomless vaginal or anal intercourse, multiple sexual partners, substance use, recreational and medical marijuana use, and tobacco and alcohol use. The frequency of disclosure of HIV status to sexual partners, and of serosorting (asking about partner's HIV status) will also be evaluated. Prevalence estimates based on those with the specific outcome of interest divided by those with measurements for that outcome along with 95% CIs will be calculated. Incidence estimates will be calculated under a Poisson distribution based on participant-years of follow-up.

The prevalence of behaviors will be compared between the YAPHIV and the YAPHEU comparison group using chi-square tests as crude analyses and using logistic regression models for each separate outcome as a function of HIV status controlling for important demographic, clinical, and social factors (socioeconomic factors, partner characteristics, viral load, adherence, and perceived social support).

Factors associated with prevalence of risk factors will be identified using logistic regression models. Factors associated with the incidence of risk behaviors including condomless vaginal or anal intercourse and substance use will be identified using Cox-proportional hazards models. Factors associated with changes in risk behaviors over time will be identified using GEE models.

12.2.9 Transition to Adult Functioning and QoL

We will estimate the prevalence of successful transition to adult functioning (including educational attainment, employment, and independent living), health-related QoL [SF-20], HIV-related stigma, mental health [CDQ, PHQ-9, and GAD-7], PTSD [Primary Care PTSD Screen for DMS-V], self-efficacy, life satisfaction, and friendship [from NIH Toolbox emotion domain] at each follow-up visit. Prevalence of milestones associated with successful adult function (including employment, educational attainment [e.g., high school diploma or general educational development (GED), enrollment in college or certificate program], independent living) will be calculated as the number of participants with each specific outcome at each visit, divided by the total number of participants who have a measure for each outcome at that

visit. The number and proportion of young adults who have met most or all of these milestones by specific ages will be estimated. The proportion of participants with psychiatric disorders and with depression (PHQ-9), anxiety (GAD-7), and PTSD will also be estimated. The 95% CIs for each prevalence estimate will be calculated. The median (interquartile range) and mean (standard deviation) scores for health-related QoL (SF-20), HIV-related stigma, self-efficacy, life satisfaction, and friendship will be calculated.

We will compare successful transition to adult functioning and QoL by perinatal HIV status and other factors using chi-square tests and Wilcoxon rank sum tests as appropriate. Factors associated with successful transition to adult function and with QoL will be further examined with univariable and multivariable logistic and linear regression models.

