9.3 Neurocognitive Functioning and Mental Health

The NIH Toolbox Cognition Battery and Emotion domain (self-efficacy, perceived social support (emotional and instrumental), friendship, and life satisfaction only) will be administered in-person at Entry and every 3 years starting at Year 3 (e.g., Year 3, 6, 9, 12, ...).

The NIH Toolbox was developed for longitudinal epidemiologic studies and prevention or intervention trials to assess cognition, sensation, motor, and emotion domains via streamlined computer-based measures. The NIH Toolbox uses Item Response Theory and Computer Adaptive Testing to provide a brief, low burden assessment with reliability and validity comparable to psychometrically sound, longer assessments. The NIH Toolbox was normed on 4859 participants (aged 3 to 85 years) representative of the U.S. population based on gender, race/ethnicity, and socioeconomic status (2010 census data). The cognitive portion of the NIH Toolbox will be proctored by centrally trained PHACS staff and does not require administration by a psychologist. The subdomains of the Cognitive portion of the NIH Toolbox include: attention, episodic memory, working memory, language, executive function, and processing speed; all these measures are either deemed important in the monitoring of HIV-related neurocognitive functioning in adults or areas of potential risk for individuals with PHIV. Scores yielded include individual measure scores as well as a Cognitive Function Composite Score, Fluid Cognition Composite Score, and Crystallized Cognition Composite Score. Measures of the Emotion domain that will be administered include self-efficacy, perceived social support (emotional and instrumental), friendship, and life satisfaction. The Emotion domain does not need to be proctored.

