12.1.2 Comparisons within YAPHIV

For the second type of comparison, subgroups of the YAPHIV will be examined. For example, comparisons can be made between those YAPHIV who initiated ART before age 5 vs. those who initiated ART at a later age. The table below summarizes the detectable differences in means relative to the standard deviation that can be detected assuming 650 YAPHIV or 415 participants (under an assumption of 4% loss per year) when two subgroups of the YAPHIV are being compared.

Table 12.2. Detectable differences in means (relative to SD) between subgroups of YAPHIV

Comparison Between Group 1 and Group 2, with indicated percentage in each group		Detectable Differences in Means (Relative to SD)	
Group 1	Group 2	N = 650	N = 415
50%	50%	0.220	0.276
40%	60%	0.224	0.281
30%	70%	0.240	0.301
20%	80%	0.275	0.345
10%	90%	0.366	0.462

Similarly, proportions with events between two subgroups of YAPHIV could be compared; for example, defined by prior receipt of cART with PI vs. cART without PI, or use of a specific ARV drug vs. unexposed to that drug. The following table provides the minimum detectable differences in terms of ORs.

Table 12.3. Detectable differences in ORs based on logistic regression models comparing two subgroups of YAPHIV with N = 650 participants or N = 415

Percent in Each group		Event Rate in Group 2	OR for Given Sample Size	
Group 1	Group 2		N = 650	N = 415
50%	50%	4%	2.59	3.20
		5%	2.38	2.89
		10%	1.93	2.25
		20%	1.68	1.90
		40%	1.56	1.75
40%	60%	4%	2.73	3.43
		5%	2.49	3.07
		10%	1.99	2.33
		20%	1.71	1.94
		40%	1.58	1.77
30%	70%	4%	3.02	3.92
		5%	2.73	3.45
		10%	2.11	2.53
		20%	1.78	2.05
		40%	1.63	1.84
20%	80%	4%	3.69	5.06
		5%	3.25	4.33
		10%	2.39	2.96
		20%	1.95	2.30
		40%	1.75	2.02

In evaluating both continuous outcomes and binary outcomes, greater power will be attained in longitudinal analyses of repeated measures over time.

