12.2.5 Reproductive Health

The analysis of reproductive health outcomes will focus on estimating the prevalence and incidence of pregnancies (intended and unintended); pregnancy outcomes (live birth, induced abortion, spontaneous abortion, fetal death); the prevalence and incidence of menstrual irregularities; and the incidence of perinatal HIV transmission.

We will calculate prevalence estimates based on those with the specific outcome of interest divided by those with measurements for that outcome, along with 95% CIs. Incidence estimates will be calculated under a Poisson distribution based on participant-years of follow-up.

The prevalence of each outcome will be compared between the YAPHIV and the YAPHEU comparison group using chi-square tests as crude analyses and using logistic regression models for each separate outcome as a function of HIV status controlling for important demographic, and clinical and social factors (including but not limited to socioeconomic factors, partner characteristics, viral load, adherence, depression, and other behaviors).

Factors associated with prevalence of each outcome will be identified using logistic regression models. Factors associated with the incidence of each outcome will be identified using Cox-proportional hazards models. Factors associated with changes in reproductive health measures over time will be identified using GEE models, or mixed effect models when possible, to account for correlation between assessments on the same participant.

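### Section 12.2.9 compares repeatedly measured adult-functioning and QoL outcomes by HIV status only with one-record-per-person methods, so it forgoes precision that a repeated-measures model would give

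*Protocol*

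**What the plan says.** Section 12.2.9 plans to estimate the prevalence or level of these outcomes repeatedly, including "self-efficacy, life satisfaction, and friendship [from NIH Toolbox emotion domain] at each follow-up visit". Milestone prevalence "will be calculated as the number of participants with each specific outcome at each visit", divided by those with a measurement at that visit. The group comparison is then stated: "We will compare successful transition to adult functioning and QoL by perinatal HIV status and other factors using chi-square tests and Wilcoxon rank sum tests". Modelling follows: "Factors associated with successful transition to adult function and with QoL will be further examined with univariable and multivariable logistic and linear regression models". The section names no GEE or mixed model and does not say which visit enters the tests or regressions. It also plans the proportion reaching most or all milestones by specific ages.

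The measurement schedule varies by outcome. Under Section 9.3 the NIH Toolbox measures, including self-efficacy, friendship and life satisfaction, "will be administered in-person at Entry and every 3 years starting at Year 3". Also, "The Client Diagnostic Questionnaire (CDQ) will be conducted in-person every 3 years starting at Year 3". The web survey is annual, but Section 9.1 allows only some topics to be asked in a given year.

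After its tables of single-time detectable differences, Section 12.1.2 adds: "In evaluating both continuous outcomes and binary outcomes, greater power will be attained in longitudinal analyses of repeated measures over time".

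**The concern.** Independent living, vocational and educational achievement, life satisfaction and health-related QoL fall under primary objective 3 (Section 2.1). Whether successful transition differs by HIV status is the first aim of Section 2.2.9. The study will hold several measurements per participant on these outcomes, yet the named methods use one at a time. The result is a series of per-visit tests for each outcome, which can disagree with one another, and each test uses only those measured at that visit.

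Visits fall on anniversaries of entry (Section 8.1) and entry is open at any age from 18, so one visit number also mixes ages. What is at stake is precision and a single clear answer to a between-group question, in a design where the comparison cohort is the smaller group.

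**Working it through.** **Inputs from Protocol Section 12.1.1.** 650 vs 200 participants give 0.227 SD, and 415 vs 101 give 0.311 SD, at 80% power and alpha 0.05 with a two-sample t-test.

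**Assumptions, not in the protocol.** There are k = 3 measured visits per participant, for example Entry, Year 3 and Year 6 for the Toolbox measures. The within-person correlation ρ is 0.5 to 0.7, with 0.9 as a high case. The outcome is a continuous score, correlation is equal between any two visits, visits are complete, and the HIV effect is constant over visits.

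**Step 1: reproduce the stated figures.** The detectable difference is (1.960 + 0.842) × √(1/n₁ + 1/n₂) in SD units.

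- 415 vs 101: 2.802 × √(1/415 + 1/101) = 2.802 × 0.1110 = 0.311.
- 650 vs 200: 2.802 × √(1/650 + 1/200) = 2.802 × 0.0809 = 0.227.

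The noncentral-t calculation gives 0.3114 and 0.2268. Both stated figures reproduce, and both are single-time figures.

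**Step 2: use all visits.** With k visits, the variance of a participant's mean is (1 + (k − 1)ρ)/k of the single-visit variance. The detectable difference is therefore multiplied by √[(1 + (k − 1)ρ)/k].

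| ρ (k = 3) | Multiplier | 415 vs 101 | 650 vs 200 | Equivalent sample, 3/(1 + 2ρ) |
|---|---|---|---|---|
| 0.5 | √(2.0/3) = 0.816 | 0.254 SD | 0.185 SD | 1.50 times |
| 0.7 | √(2.4/3) = 0.894 | 0.278 SD | 0.203 SD | 1.25 times |
| 0.9 | √(2.8/3) = 0.966 | 0.300 SD | 0.219 SD | 1.07 times |

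Over a wider range (k from 2 to 4, ρ from 0.3 to 0.8), the 415 vs 101 figure runs from 0.214 SD (k = 4, ρ = 0.3) to 0.295 SD (k = 2, ρ = 0.8).

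**Step 3: express it as power.** At a true difference of 0.311 SD with 415 vs 101, power is Φ(2.802/multiplier − 1.960).

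- ρ = 0.5: Φ(3.43 − 1.96) = 93%.
- ρ = 0.7: Φ(3.13 − 1.96) = 88%.
- A single visit gives 80%.

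**Step 4: simulation check.** With 650 vs 200, three visits, ρ = 0.5 and 4,000 datasets, power at 0.227 SD was 80% at a single visit and 93% with participant-level averages. Type I error was 5.0% and 5.3% respectively.

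**The case against.** The strongest reply is that nothing in Section 12.2.9 is wrong. The aim is a comparison by HIV status, not a question about change over time, and a chi-square, Wilcoxon or ordinary regression analysis at one visit answers it validly. Which visit to use can be settled in a statistical analysis plan. All of this stands, and it is why the point is one of precision rather than validity.

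Four stronger readings are tempting, and the protocol does not support them.

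- *That Section 12.1 promises a repeated-measures power which is then lost.* Its mean-difference figures are single-time, and a single-visit comparison with the stated numbers attains them. The sentence on longitudinal analyses carries no figure and does not promise such an analysis in every domain.
- *That all these outcomes are collected at every visit.* The Toolbox measures and the CDQ are three-yearly, and survey topics may be a subset in a given year.
- *That neighbouring domains use GEE for this same comparison.* Section 12.2.5 does name "GEE models, or mixed effect models when possible, to account for correlation between assessments on the same participant", but for changes over time, as do Sections 12.2.7 and 12.2.8. For prevalence by HIV status, 12.2.5 and 12.2.8 use chi-square tests and logistic regression, much as 12.2.9 does.
- *That visits will be pooled as if independent, raising the false-positive rate.* No such pooling is planned; the prevalences are explicitly per visit.

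Two further limits stand. The trajectory models in Section 12.2.6 already cover depression, anxiety and PTSD, though not milestones, SF-20 QoL, life satisfaction or friendship. And attainments such as a diploma stay met once reached, so their within-person correlation may be high and the gain small.

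**Conclusion.** The point holds as an improvement. For outcomes measured at several visits, Section 12.2.9 names only one-record-per-person methods for the comparison by HIV status, so as written it yields separate per-visit tests and forgoes the extra precision of a longitudinal analysis. Under the stated assumptions the forgone gain for 415 vs 101 is a fall in detectable difference from 0.311 SD to about 0.25–0.28 SD, shrinking to about 0.30 SD at a correlation of 0.9.

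The size depends on the assumed number of visits and correlation, neither of which the protocol gives. It is worked for continuous scores with complete visits and no covariate adjustment. Incomplete visits would reduce the gain, and the figures do not carry over directly to binary milestones.

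**What to change.** In Section 12.2.9, name as the main comparison by HIV status one model per outcome across all available visits: a GEE with robust variance, or a mixed model. Use a logit link for binary milestones and an identity link for scores. Include HIV status, age and visit as terms, and add HIV status by age where the difference may vary with age. Keep the per-visit prevalences, chi-square tests and Wilcoxon tests as description.

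The cost is a change of wording and slightly more programming. No new data are needed, and these model types already appear elsewhere in Section 12.2. The drawback is that, without the age interaction, the estimate is an effect averaged over visits and ages rather than a difference at one point; the text should say so.
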